Orginal Title: Evaluation of Anthropometric and Ultrasonographic Measurements With Different Machine Learning Methods in Predicting Difficult Intubation: A Prospective Observational Study

Brief Title: Anthropometric and US-Guided Difficult Intubation Prediction With ML Models

NCT Number: NCT06904586

UPDATE DATE: 20.04.2025

ETHICS APPROVAL DATE: 18.04.2022

Statistical Analysis Plan

It is reported in the literature that the rate of difficult intubation is approximately 17% (3). This study determined the minimum sample size required to detect a statistically significant difference (effect size= 0.1) as 273 individuals under 95% power and 5% type I error conditions. Power analysis was performed with the PASS v.15 demo program.

Machine Learning Algorithms

The data labeled with expert opinion on whether there was a difficult intubation was classified using 8 different machine learning algorithms, which are among the most widely used classification algorithms in the literature and have proven success in this field. These algorithms are; Logistic Regression (LR) , Support Vector Machine (SVM) , Random Forest (RF), K-Nearest Neighbors (KNN), Gaussian Naive Bayes (GNB) , CatBoost, XGBoost ve Decision Tree (DT). These algorithms were applied to the dataset, and the results were obtained.

The 15 most affecting features determined by the feature extraction method from the 30 parameters in the dataset were selected and the dataset was prepared for the classification process according to these features. In addition, different pre-processing methods, such as editing and categorizing the "null" values, were applied to the dataset.

Models were created for each algorithm. The data set was evaluated in 2 groups: 80% training and 20% testing. After training and testing each model with data, the results were obtained. K-fold Cross-validation, the training data is divided into k equal parts. The divided parts are used for both training and testing. 5-Fold cross-validation was performed on the training data. This prevented overfitting of the data.

PROTOCOL

Ethics committee approval numbered 2022/65 was received from the Düzce University Non Interventional Health Research Ethics Committee. Our study, which received project support numbered 2023.04.04.1402 from Düzce University Scientific Research Projects Coordinatorship, was designed as a prospective, observational study in the Anesthesiology and Reanimation Clinic of the Faculty of Medicine Hospital. Informed consent was obtained from all patients.

Patients over the age of 18 who underwent general anesthesia and had an American Society of Anesthesiologists (ASA) score between I-III were included in the study. Patients who had undergone or were planned to undergo head and neck surgery, who were scheduled to undergo thyroidectomy, who had congenital or acquired morphological disorders, and who had a history of difficult airways were excluded from the study.

It is reported in the literature that the rate of difficult intubation is approximately 17%. This study determined the minimum sample size required to detect a statistically significant difference (effect size= 0.1) as 273 individuals under 95% power and 5% type I error conditions. Power analysis was performed with the PASS v.15 demo program.

329 patients who met the inclusion criteria were included in the study. Following routine vital monitoring (ECG, SpO₂, NIBP) in the preoperative evaluation room, age, gender, weight, height, body mass index (BMI), Modified Mallampati score, and upper lip bite test (ULBT) values were recorded.

Anthropometric lengths were measured as described with the help of a tape measure;

1. Thyromental distance: the distance from the thyroid notch to the lower tip of the chin when the patient's head is in a neutral position
2. Neck circumference: the measurement around the entire neck with the help of a tape measure, just below the thyroid cartilage
3. Mouth opening distance: the distance between the upper and lower incisors at maximum mouth opening
4. Sternomental distance: the length from the sternal notch to the mentum when the neck is extended

The ultrasonic evaluation was performed with the 4- 15 MHz linear probe of the Esaote MayLab sevenR ultrasound in the supine position, with the head and neck in a neutral position. The distances

to the anterior neck surface were obtained by placing the linear probe in a transverse position at three different levels;

1. Minimum distance from the hyoid bone to the skin surface (DSHB) at the level of the hyoid bone
2. Distance from the skin to the epiglottis (DSE) at the midpoint between the hyoid bone and the thyroid cartilage at the level of the thyrohyoid membrane
3. Minimum distance from the skin to the vocal cord anterior commissure (DSAC) at the level of the anterior commissure
4. Distance between the skin and the trachea (DST) 2 cm above the sternal notch, with the trachea seen transversely
5. Maximum tongue thickness in the sagittal axis under the chin with a 1- 8 MHz convex probe while the patient was in the neutral position.
6. The distance from the hyoid bone shadow to the mentum via the convex probe while the patient's neck is in extension (DSHBE) and neutral (DSHBN) positions. All USG evaluations were performed by an independent trained anesthesiologist.

Patients were induced with 2-2.5 mg/kg propofol, 1 mcg/kg fentanyl and 0.6 mg/kg rocuronium.

Mask-ventilated patients were intubated by direct laryngoscopy by an anesthesiologist with different professional experience after the count became 0 with neuromuscular monitoring using GE Healthcare's line of NMTR accessories. Cormack-Lehane score was recorded. Patients who could not be intubated were taken over by more experienced specialist physicians. Patients who could not be intubated by direct laryngoscopy by an anesthesiologist with 5 years or more experience, who used video laryngoscopy, fiberoptic bronchoscopy, and who required stylet, bougie, and cricoid pressure in addition to video laryngoscopy were evaluated as having difficult intubation.

The data obtained from the patients were subjected to various pre-processing steps to make them suitable for classification. Although there are many methods for pre-processing, the pre processing steps applied to the data set used in this study were the editing of null data, categorization of data, and feature extraction. After the completion of the null data, the textual data in the data set was converted to categorical data. Since there was little difficult intubation data in the data set, data augmentation was performed to prevent memorization in the data.

Data balancing was performed for the difficult intubation class, which was in the minority, using SMOTE (Synthetic Minority Over-Sampling Technique). SMOTE increased the samples of the minority classes and balanced the unbalanced classes.

Machine Learning Algorithms

The data labeled with expert opinion on whether there was a difficult intubation was classified using 8 different machine learning algorithms, which are among the most widely used classification algorithms in the literature and have proven success in this field. These algorithms are; Logistic Regression (LR), Support Vector Machine (SVM), Random Forest (RF), K-Nearest Neighbors (KNN), Gaussian Naive Bayes (GNB) , CatBoost, XGBoost ve Decision Tree (DT). These algorithms were applied to the dataset, and the results were obtained.

The 15 most affecting features determined by the feature extraction method from the 30 parameters in the dataset were selected and the dataset was prepared for the classification process according to these features. In addition, different pre-processing methods, such as editing and categorizing the "null" values, were applied to the dataset. Models were created for each algorithm. The data set was evaluated in 2 groups: 80% training and 20% testing. After training and testing each model with data, the results were obtained. K-fold Cross-validation, the training data is divided into k equal parts. The divided parts are used for both training and testing. 5-Fold cross-validation was performed on the training data. This prevented overfitting of the data.

FLOW CHART

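### The plan names no result that isolates what the anthropometric and ultrasonographic measurements contribute: one pooled set of 15 features is chosen from 30 unlisted parameters, and only the algorithm is varied

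*Combined protocol and SAP*

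**What the plan says.** The full title reads "Evaluation of Anthropometric and Ultrasonographic Measurements With Different Machine Learning Methods in Predicting Difficult Intubation". The measurements are what is evaluated, and the algorithms are the means.

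The Machine Learning Algorithms section appears in both the Statistical Analysis Plan and the Protocol, with the same content. It states that the 15 leading features "determined by the feature extraction method from the 30 parameters in the dataset were selected". It continues that "the dataset was prepared for the classification process according to these features", and then "Models were created for each algorithm". An 80/20 split and 5-fold cross-validation of the training part follow. No performance metric is named.

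The Protocol describes three kinds of preoperative variable:

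- **Demographic, body-size and bedside items:** "age, gender, weight, height, body mass index (BMI), Modified Mallampati score, and upper lip bite test (ULBT) values were recorded".
- **Tape measurements:** "Anthropometric lengths were measured as described with the help of a tape measure", followed by four items.
- **Ultrasound measurements:** six numbered items, beginning with "Minimum distance from the hyoid bone to the skin surface (DSHB) at the level of the hyoid bone". The sixth gives two values (neck extended and neck neutral), so there are seven measurements.

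The 30 parameters are not listed anywhere.

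**The concern.** The only thing that varies between the eight results is the algorithm. No model is stated for tape measurements, ultrasound measurements or bedside items alone, and none for one group added to another. No result per measurement, such as an AUC, a cut-off or an odds ratio, is stated either.

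A good pooled result would naturally be read as support for tape and ultrasound measurement. It could equally come mostly from Mallampati, upper lip bite test, age and gender, which were recorded in the same patients. The distinction matters in practice, because the ultrasound examination uses two probes and an independent trained anesthesiologist. The 80/20 split and the cross-validation cannot settle it, since both act on the same mixed feature set.

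**Working it through.** **1. Count of described variables (Protocol).**

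- Tape: thyromental, neck circumference, mouth opening, sternomental = 4.
- Ultrasound: DSHB, DSE, DSAC, DST, tongue thickness, DSHBE, DSHBN = 7.
- Tape plus ultrasound: 4 + 7 = 11. With weight, height and BMI: 11 + 3 = 14.
- With age, gender, Mallampati and upper lip bite test: 14 + 4 = 18.
- ASA class and Cormack-Lehane score are also mentioned (20 in all), but the documents do not say that either was a candidate.

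**2. Attempt to rebuild the 30.** The figure cannot be reproduced. Between 30 − 20 = 10 and 30 − 18 = 12 parameters are not described.

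**3. What the count allows.** Assume that the 18 described preoperative items are all among the 30, and count body size as anthropometric. If none of the 12 others is a tape, body-size or ultrasound value, 30 − 14 = 16 candidates lie outside the titled measurements. If all 12 are such values, 30 − 26 = 4 lie outside. Without body size, the same two limits are 30 − 11 = 19 and 30 − 23 = 7. The documents do not fix the share more closely than this.

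**4. Why a pooled result does not answer the title (illustration; every input is assumed).** The documents give no performance figure, so AUC is taken as the metric. Treat the bedside group and the measurement group as two normally distributed scores with within-class correlation r:

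- separation of one score: d = √2 · Φ⁻¹(AUC)
- separation of the best combination: D² = (d₁² + d₂² − 2·r·d₁·d₂) / (1 − r²)
- pooled AUC = Φ(D/√2)

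An AUC of 0.60 gives d = 0.358, and an AUC of 0.80 gives d = 1.190. With r = 0, D = √(0.358² + 1.190²) = 1.243, and the pooled AUC is 0.810.

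| Bedside alone | Measurements alone | Pooled | Gain from adding measurements |
|---|---|---|---|
| 0.60 | 0.80 | 0.81 | 0.21 |
| 0.80 | 0.60 | 0.81 | 0.01 |

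The pooled figure is identical in the two rows, while the conclusion about the measurements is opposite. With each group's AUC between 0.60 and 0.80 and r = 0, 0.3 or 0.5, the gain ranges from 0.00 to 0.21.

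**5. Which data should carry the comparison (also assumed).** At the 17% rate in the sample-size statement, 329 patients give 329 × 0.17 ≈ 56 difficult intubations. The 20% test set (329 × 0.2 ≈ 66 patients) gives about 11. In 4,000 simulated data sets with bedside AUC 0.70, measurement AUC 0.75 and independent scores, the mean gain was 0.10. Its standard error was about 0.032 with all 329 patients and about 0.075 with a 66-patient test set. These scores are taken as known; fitting the models would add uncertainty.

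**The case against.** Four objections carry weight.

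- **The count alone proves nothing.** If all 30 candidates were tape or ultrasound values, a single pooled model would still credit none of them. Conversely, nested models could isolate 14 among 30 without difficulty. This stands: the gap is the missing group-wise analysis, and the count only shows that the pool is mixed.
- **The selection step ranks features.** It therefore gives some information on the measurements relative to the bedside items. This stands in part. The selection method is unnamed, no importance output is stated, and a rank within a pool does not give the gain over another group.
- **The title may mean joint prediction with several algorithms.** That is a fair reading, and no stated objective asks for incremental value over bedside tests. Even so, the joint model would then be expected to be a model of the titled measurements, and the plan does not restrict it to them.
- **The AUC figures are assumed.** They are. They show that a pooled result is ambiguous, not what this dataset would yield.

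A reader might go further and infer that 16 to 19 of the 30 candidates lie outside the titled measurements, so that at least 1 to 4 of the 15 kept features must do so. The documents do not support this. The 10 to 12 undescribed parameters could be derived or repeated measurements, and the forced minimum can be zero. Nor do the documents support saying that the plan reports only accuracy, since it names no metric, or that it is incapable of evaluating the measurements.

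**Conclusion.** The point holds in this form: no stated result isolates the predictive value of the tape or ultrasound measurements, although the title presents them as what is evaluated. This rests on the text alone. One set of 15 is drawn from a pool of 30, the algorithm is the only factor varied, and age, gender, Mallampati and upper lip bite test are recorded alongside the 11 to 14 described measurements.

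The size of the ambiguity can only be illustrated: a gain anywhere from 0.00 to 0.21 in AUC, under two normal scores with assumed AUCs of 0.60 to 0.80 and correlation up to 0.5. The share of candidates outside the measurements remains unknown until the 30 are listed. The point should be acted on because a small added analysis lets the study answer its own title; the pooled models are not thereby shown to be wrong.

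**What to change.** 1. List the 30 candidates by source and by time of measurement.
2. Define nested feature sets: (A) demographic and bedside items; (A+B) plus tape and body-size measurements; (A+B+C) plus ultrasound measurements. State in which group Mallampati and upper lip bite test are placed.
3. Fit the sets on identical resampling splits. Carry out null-value completion, feature selection and SMOTE only inside each training fold, so that held-out patients do not influence them.
4. Name one primary algorithm and one metric in advance, for example AUC. Otherwise two differences for each of eight algorithms give 16 contrasts with no rule for choosing among them.
5. Report A+B minus A, and A+B+C minus A+B, as paired differences with confidence intervals, from out-of-fold predictions on all 329 patients.
6. Keep the other algorithms and the pooled top-15 comparison as secondary results.

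The cost is three feature sets in place of one, plus a table of candidates, all on existing data. The sponsor must accept that the gain attributable to tape or ultrasound measurement may turn out small.

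### A single 20% hold-out (about 66 patients, about 11 events at 17%) is too small to evaluate eight algorithms; repeated cross-validation on all 329 would about halve the uncertainty

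*Combined protocol and SAP*

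**What the plan says.** The Machine Learning Algorithms text, which appears in both the Statistical Analysis Plan and the Protocol, applies eight classifiers and states: "The data set was evaluated in 2 groups: 80% training and 20% testing". It continues: "After training and testing each model with data, the results were obtained". Cross-validation is confined to the training part and given one purpose: "5-Fold cross-validation was performed on the training data. This prevented overfitting of the data".

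The Protocol gives the cohort size, "329 patients who met the inclusion criteria were included in the study", and the sample-size paragraph uses a literature rate of difficult intubation of about 17%. No observed event count is given. The pre-processing paragraphs indicate only that it was low ("Since there was little difficult intubation data in the data set") and that oversampling was used: "SMOTE increased the samples of the minority classes and balanced the unbalanced classes". Whether SMOTE came before or after the split is not stated.

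The documents name no performance measure and mention no stratification of the split, repeated splits, confidence intervals or method for comparing the algorithms.

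**The concern.** How well the algorithms predict difficult intubation is the study's main result. If it is read from one fifth of the cohort, the effective sample size is the number of difficult intubations in that fifth. With about 11, one patient moves sensitivity by 1/11, or 9 percentage points.

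The documents do not say that a best algorithm is declared. But the title announces "Evaluation of Anthropometric and Ultrasonographic Measurements With Different Machine Learning Methods in Predicting Difficult Intubation", so eight results will be read side by side. A reader could take a chance spread for a real difference. Even without any ranking, each algorithm's own sensitivity would be very imprecise. The data already collected can do better, because the other four fifths contribute nothing to the hold-out estimate.

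**Working it through.** **Inputs.** From the documents: 329 patients, 20% test share, 17% event rate (literature), eight algorithms. Assumed, because the documents do not give them: AUC as the measure, true AUC 0.80, true sensitivity 80%, correlation 0.5–0.9 between algorithms' scores, and a 10% event rate as a lower alternative. The plan gives no precision figure for the hold-out, so there is none to reproduce. Its sample size of 273 does not address this question.

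**1. Size of the hold-out.** 0.20 × 329 = 65.8, about 66 patients. At 17%: 0.17 × 65.8 = 11.2 events. At 10%: 6.6 events. The whole cohort at 17% has 0.17 × 329 = 55.9, about 56 events. If the split is not stratified, the hypergeometric 95% range (66 drawn from 329 with 56 events) is 6–17 events; at 10% (33 events) it is 3–11.

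**2. Sensitivity (Clopper–Pearson 95% interval).** Hold-out, 9/11: 48–98%. All 329, 45/56: 68–90%.

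**3. AUC.** Hanley–McNeil variance, with n₁ events and n₀ non-events:

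Var = [A(1−A) + (n₁−1)(Q₁−A²) + (n₀−1)(Q₂−A²)] / (n₁n₀), where Q₁ = A/(2−A) and Q₂ = 2A²/(1+A).

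At A = 0.80, Q₁ = 0.6667, Q₂ = 0.7111 and A² = 0.64. Hold-out: [0.16 + 10 × 0.0267 + 54 × 0.0711] / 605 = 4.267/605 = 0.00705, so SE = 0.0840. The equal-variance binormal model replaces both Q terms by 0.687. Half-width = 1.96 × SE:

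| Basis | Events / non-events | SE, binormal / Hanley–McNeil | 95% half-width |
|---|---|---|---|
| Hold-out, 17% | 11 / 55 | 0.0725 / 0.0840 | 0.142 / 0.165 |
| Hold-out, 10% | 7 / 59 | 0.0877 / 0.1037 | 0.172 / 0.203 |
| Existing 5-fold, training part, 17% | 45 / 218 | 0.0356 / 0.0413 | 0.070 / 0.081 |
| All 329, 17% | 56 / 273 | 0.0319 / 0.0370 | 0.063 / 0.073 |

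The last two rows treat out-of-fold predictions as if they came from one fixed model; step 5 drops that simplification. The ratio expected from sample size alone is √(66/329) = 0.45.

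**4. Ordering eight algorithms.** Binormal simulation, hold-out of 11/55, 4,000 runs:

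| Score correlation | 0.5 | 0.7 | 0.9 |
|---|---|---|---|
| Eight equal: median best-to-worst sensitivity spread | 0.273 | 0.273 | 0.182 |
| Eight equal: median best-to-worst AUC spread | 0.149 | 0.117 | 0.069 |
| Eight equal: excess of the best AUC over the truth | 0.074 | 0.059 | 0.038 |
| One at 0.85, seven at 0.80: it ranks first | 36% | 45% | 71% |
| One at 0.90, seven at 0.80: it ranks first | 75% | 86% | 99% |

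At 10% (7/59) the last two rows become 32–61% and 62–96%. With 56/273 and a fixed model (600 runs), the median sensitivity spread falls to 0.125–0.089, and the algorithm at 0.85 ranks first in 76–99.5% of runs.

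**5. Gain when models are refitted in each fold.** Simulated cohorts of 329 with 15 correlated features and SMOTE in training data only; logistic regression, Gaussian naive Bayes and KNN; true AUC 0.75–0.81; error measured against the fitted model's true AUC. Entries are 1.96 × RMSE:

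| Quantity | Hold-out | 4 × 5-fold on all 329 |
|---|---|---|
| AUC, 17% (2,051 runs) | 0.144–0.152 | 0.067–0.073 |
| Gap between two algorithms, 17% | 0.101–0.114 | 0.053–0.061 |
| AUC, 10% (2,057 runs) | 0.181–0.199 | 0.087–0.095 |

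A second simulation with a different data model and 10 × 5-fold cross-validation (400 cohorts, three simple classifiers) gave an RMSE ratio to the hold-out of 0.50–0.57. Both support a reduction of about half.

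**6. If SMOTE to 1:1 came before the split.** 2 × 273 = 546 records, where 273 is now the number of non-events (329 − 56). Of these, 546 − 329 = 217 (40%) are synthetic. A 20% test part has about 109 records, about 43 of them synthetic. The precision figures above do not describe such a test set.

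**The case against.** The arithmetic is not in dispute. The strongest case concerns the baseline and how the results will be used.

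- **Cross-validation is already in the plan.** Against it, rather than the hold-out, moving to all 329 gains only about 10% (0.063/0.070 and 0.073/0.081 are both 0.90), and repeats add a little more. This stands: most of the precision would come from making cross-validation the reported estimate. The halving is relative to the hold-out. The plan credits the 5-fold step only with preventing overfitting and does not make it the performance estimate. If feature selection or SMOTE preceded the folds, it would need re-running anyway.
- **The documents do not say outright which estimate is presented.** True. The hold-out is the natural reading of an 80/20 split into training and testing.
- **Ranking is not a stated aim, and coming first of eight is a severe criterion.** Also true. For one pair with a 0.05 gap (0.80 against 0.85), a normal approximation with correlation 0.3–0.8 between the two AUCs puts the hold-out order right in 70–84% of cases, against 89–99% with 329. That is less stark but still weak, and the width of each sensitivity interval does not depend on ranking.
- **The fix leaves a gap error of ±0.05–0.06, so a 0.05 difference remains within error.** This stands. So does the limit that only simple classifiers were refitted; SVM and the tree-based methods are extrapolated.
- **A locked test set is a recognised design, and a change now is post hoc.** Both are real costs. The minimum version of the fix keeps the locked set.

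**Conclusion.** The concern holds, and the plan should be changed. One 20% hold-out of about 66 patients, with about 11 events if the 17% rate applies, gives an AUC error of about ±0.14 to ±0.16 and a sensitivity interval about 50 points wide. It cannot reliably order modest differences (an AUC gap near 0.05), although a gap of 0.10 would usually be seen. Repeated cross-validation on all 329 roughly halves that error, to about ±0.07, without making small gaps conclusive.

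Confidence is moderate. The event count comes from a planning rate; at 10% the hold-out is worse (about ±0.17 to ±0.20). The AUC level, score correlations and simulated data are assumptions. If SMOTE preceded the split, these precision figures do not apply and synthetic test records become the first problem; the same fix removes it.

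**What to change.** **Preferred.** Make the main performance estimate outcome-stratified, repeated 5-fold cross-validation on all 329 real patients. Do null handling, selection of the 15 features, SMOTE and any tuning only inside the training folds, so that every test record is a real patient. Report out-of-fold AUC, sensitivity and specificity with 95% confidence intervals for all eight algorithms, and paired intervals for their differences. If one algorithm is put forward as best, choose it in an inner loop.

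**Minimum, if the split is kept.** Stratify it by outcome and make it before SMOTE. Compare and choose algorithms on the 5-fold results, and report the chosen algorithm's hold-out result with its confidence interval.

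In either case, label the work as a re-analysis, since results have already been obtained.

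**Cost.** No new patients. The preferred version needs a re-run on the collected data, more computing time and revised SAP wording; the minimum needs one re-run and a few sentences. The preferred version gives up a single locked test set, and its confidence intervals are approximate.

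### Five-fold cross-validation cannot itself prevent overfitting, and it estimates it reliably here only if feature selection and SMOTE stayed inside the training folds, which the plan does not say

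*Combined protocol and SAP*

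**What the plan says.** The section Machine Learning Algorithms appears in both the SAP and the protocol, and both versions end with the same two sentences: "5-Fold cross-validation was performed on the training data", followed by "This prevented overfitting of the data". Neither says that the folds were used to tune a model, choose a penalty or depth, or set the number of features.

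The same section gives the hold-out: "The data set was evaluated in 2 groups: 80% training and 20% testing". Before that it describes feature selection: "The 15 most affecting features determined by the feature extraction method from the 30 parameters in the dataset were selected", after which "the dataset was prepared for the classification process according to these features".

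The protocol's pre-processing paragraphs, placed just before its Machine Learning Algorithms section, list null editing, categorization and feature extraction as steps on the data set. They then say that, because difficult intubations were few, "data augmentation was performed to prevent memorization in the data". On balancing they say: "SMOTE increased the samples of the minority classes and balanced the unbalanced classes". The SAP does not mention SMOTE. Neither document says whether any of these steps was restricted to training patients or training folds.

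**The concern.** There are two separate problems.

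**The claim is wrong whatever the order of steps.** Cross-validation refits a given model on part of the data and scores the remainder. The final model is the same as if the folds had never been run, unless the scores are used to choose how complex it should be. Without such a use, cross-validation can show overfitting but cannot prevent it.

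**In the narrated order, the folds may not show it either.** If features are ranked on outcomes that include the held-out patients, the held-out score is somewhat optimistic. If SMOTE runs before the folds, the effect is much larger. Each synthetic difficult-intubation record is interpolated between real ones, so records in the validation fold have close relatives in the training folds. A flexible algorithm can then score well by recognising those relatives.

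At stake is whether the performance figures for the eight algorithms can be taken at face value. A reader told that overfitting was prevented has little reason to ask how the held-out data were protected.

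**Working it through.** The documents give no figure for accuracy or overfitting, so there is no stated result to reproduce. The check asks what the described procedure returns when there is nothing to find.

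**Inputs from the documents:** 329 patients; 30 candidate features, 15 kept; 80/20 split; 5 folds; SMOTE until the classes are balanced; eight algorithms.

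**Assumed:** the event rate. The protocol cites 17% from the literature and does not give the observed count. Rates of 10% and 5% were also run.

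**Counts that follow:**
- Events: 0.17 × 329 = 55.9, about 56. At 10%, 32.9, about 33. At 5%, 16.5, run as 16.
- Training set: 0.80 × 329 = 263. Test set: 329 − 263 = 66.
- Training events at 17%: 0.17 × 263 = 44.7, about 45. Test events: 0.17 × 66 = 11.2, about 11.
- Balancing the training set: 263 − 45 = 218 non-events, so 218 − 45 = 173 synthetic events. Then 173/218 = 79% of the event records are synthetic.
- Each synthetic record has two real parents. If folds are assigned at random, the chance that both parents fall in the record's own fold is about (1/5)² = 0.04. So about 96% of synthetic records have at least one parent in the folds used for training.

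**Simulation.** The features were 30 variables unrelated to outcome, so the true AUC is 0.50. The 15 with the largest univariate F or t statistic were kept, and SMOTE used 5 neighbours. AUC runs used 40 to 100 simulated data sets and covered logistic regression and KNN in each, with random forest and decision tree in the 40-set run. Accuracy runs used 20 data sets at 17% and 8 each at 10% and 5%. They covered six of the named algorithms, with gradient boosting standing in for XGBoost and CatBoost.

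*Step 1: does running the folds change the fit?* No. Models fitted on the 263 training patients had training AUC 0.73 (logistic), 0.82 (KNN) and 1.00 (random forest and tree). AUC in new patients was 0.50 for all four.

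*Step 2: what do the folds and the test set show, by order of steps (17% events)?*

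| Order | 5-fold AUC | 20% test set AUC |
|---|---|---|
| Selection and SMOTE before the split | inflated (accuracy row below) | about 0.70 logistic, 0.88 KNN |
| Selection on all data, SMOTE on training patients before the folds | about 0.70 logistic, 0.78 tree, 0.87 KNN, 0.96 random forest | about 0.50 to 0.59 (real patients) |
| Selection on all data, SMOTE inside the folds | about 0.54 to 0.58 | – |
| Everything inside the folds | about 0.50 | – |

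The accuracy runs agree:

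| Order | 5-fold result | 20% test set |
|---|---|---|
| Selection and SMOTE before the split | accuracy 0.65 (logistic) to 0.87 (random forest) | accuracy 0.90 for random forest |
| SMOTE on training patients before the folds | accuracy 0.66 (logistic) to 0.90 (random forest) | balanced accuracy 0.50 to 0.55 on real patients |
| Everything inside the folds | balanced accuracy 0.49 to 0.51 | – |

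*Step 3: fewer events.* With SMOTE before the split, 5-fold accuracy for random forest on noise rises from 0.87 at 17% to 0.93 at 10% and 0.98 at 5%. For logistic regression it rises from 0.65 to 0.72 and 0.82.

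**The case against.** The best defence is that the sentence is loose wording for a normal workflow, and that the rest depends on an order of steps nobody has stated. Much of this stands, and four stronger readings should be set aside.

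- **That cross-validation is the plan's only safeguard.** It is not. The 80/20 hold-out is stated, and so is augmentation with an explicit anti-memorization purpose. Either may be weak, but both are there. Augmentation did not help on noise: random forest, boosting and tree fitted to the SMOTE-balanced training set still reached training accuracy 1.00.
- **That leakage occurred.** The text narrates selection and SMOTE before the split and folds, but order of narration is not proof of order of execution. If SMOTE ran inside the folds, only the modest selection bias remains.
- **That the folds could never reveal overfitting.** With selection on all data and SMOTE inside the folds, training AUC of 0.73 to 1.00 set beside 5-fold AUC of 0.54 to 0.58 would show it plainly. The folds fail badly only when SMOTE precedes them.
- **That the published performance is necessarily optimistic.** The documents name no performance metric and do not say whether fold or test results are the headline. If SMOTE was applied to training patients only, the real test set would largely expose the problem, though with only about 11 events at 17%.

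The defence does not rescue the claim itself, which is wrong under every order. Nor does it supply the missing statement of which patients informed selection and balancing.

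**Conclusion.** The concern holds in conditional form. The statement that cross-validation prevented overfitting is incorrect in both places and should not stand. Beyond wording, the procedure as narrated can return a 5-fold AUC of about 0.70 to 0.96 on data with no signal. It can also inflate the test set if balancing came before the split. If balancing was kept inside the folds, the excess is about 0.04 to 0.08 in AUC (0.54 to 0.58 against 0.50). If every step was inside, there is essentially none.

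These sizes rest on the 17% literature rate, independent features with no signal, univariate feature ranking, default model settings and a stand-in for two of the algorithms. The direction was the same for every algorithm run with SMOTE before the folds, and the inflation grew with fewer events. The figures show how far the method can mislead; they do not estimate the optimism in this study's own results.

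**What to change.** 1. Delete the claim in the SAP and in the protocol, and say instead that cross-validation estimates performance in patients not used for fitting.
2. State the order of steps. Make the 80/20 split first, on real patients.
3. Refit null filling, feature selection and SMOTE inside each training fold. For the final model, fit them on the training set only. Keep the validation folds and the 20% test set as real, unbalanced patients.
4. For each algorithm, report training, cross-validated and test performance side by side, with the observed number of events in each set. Base conclusions on the held-out values.

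The cost is a text correction, a rerun on existing data and one table; no new patients are needed. The downside is that reported performance will probably look less favourable. If the steps were already confined to training folds, stating so and removing the claim is enough, apart from the table.
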